#### 3.3 CLINICAL ASSESSMENTS

#### 3.3.1 Efficacy

#### 3.3.1.1 Six-Minute Walk Test (6MWT)

The 6MWT is a validated and reliable measure of exercise capacity in patients with chronic respiratory diseases (Holland 2014). This study will utilize an unencouraged peak 6MWT to minimize potential bias associated with encouragement. All 6MWTs will be conducted by qualified, trained personnel in a designated 6MWT area which meets the requirements as described in Appendix 15.1. Prior to the start of each 6MWT the subject must rest (seated) for at least 10 minutes. The peak 6MWT must be conducted between 10 to 60 minutes after the most recent dose of study drug.

A peak 6MWT will be conducted at Baseline as part of the Study Termination (Week 16) assessments from protocol RIN-PH-201. A peak 6MWT will also be performed at Week 4, Week 12, every 12 weeks thereafter, and at Week 108/Study Termination.

#### 3.3.1.2 St. George's Respiratory Questionnaire

The SGRQ will be conducted at Baseline as part of the Study Termination (Week 16) assessments from protocol RIN-PH-201. The SGRQ will also be conducted at Week 48 and at Week 108/Study Termination. The SGRQ should be completed as the first assessment during these visits before the subject completes any of the other scheduled visit assessments. A copy of the SGRQ can be found in Appendix 15.3.

#### 3.3.1.3 N-terminal pro-brain natriuretic peptide (NT-proBNP)

Plasma NT-proBNP concentration is a useful biomarker associated with changes in right heart morphology and function (Fijalkowska 2006). NT-proBNP sample collection will occur at Baseline as part of the Study Termination (Week 16) assessments from protocol RIN-PH-201. NT-proBNP will also be collected at Week 48 and at Week 108/Study Termination. Blood for NT-proBNP assessment must be drawn prior to conducting the 6MWT.

#### 3.3.1.4 Optional Biomarker

For subjects consenting to the optional biomarker sample, blood will be collected for the evaluation of biomarkers (specific targets to be determined) at Baseline as part of the Study

Termination (Week 16) assessments from protocol RIN-PH-201 and at Week 48 (or upon early termination if prior to Week 48).

#### 3.3.1.5 Change in DSP

Change in DSP is the product of distance walked and lowest oxygen saturation recorded during the 6MWT. This assessment has been shown to be predictive of mortality in patients with idiopathic pulmonary fibrosis and as such will be evaluated as an exploratory endpoint in this study (Lettieri 2006). Change in DSP will be calculated from Baseline to Week 4, Week 12, every 12 weeks thereafter, and at Week 108/Study Termination.

#### *3.3.2 Safety*

During this study, treatment emergent changes in physical examination (PE) findings, vital signs, clinical laboratory parameters, PFTs, oxygenation, hospitalizations due to a cardiopulmonary indication, exacerbations of underlying lung disease, and the development of AEs after treatment will be the primary assessments of safety.

#### 3.3.2.1 Physical Examinations

A complete physical examination (PE) will be conducted during Baseline as part of the Study Termination (Week 16) assessments from protocol RIN-PH-201. A follow-up PE will also be performed at the Study Termination Visit. Any clinically significant changes from Baseline noted during the course of the study or during the Study Termination PE should be reported as AEs.

#### 3.3.2.2 Vital Signs

Vital signs will be assessed at Baseline as part of the Study Termination (Week 16) assessments from protocol RIN-PH-201 and at each subsequent study visit and at the Study Termination Visit. Vital signs measured will include blood pressure (systolic and diastolic), heart rate (HR), respiratory rate (RR), temperature, and weight. Vital signs must be assessed following at least five minutes of rest (sitting) to ensure accurate measurement. No other measurements or procedures should be performed during this five-minute period. When applicable, vital signs should be collected prior to the 6MWT. If vital signs cannot be obtained prior to the 6MWT, they should be obtained after recovery from the 6MWT. Vital signs should also be assessed in the case of abnormal clinical signs and symptoms.

#### 3.3.2.3 Clinical Laboratory Assessments

Clinical laboratory parameters will be assessed at Baseline as part of Study Termination assessments from protocol RIN-PH-201. Clinical laboratory assessments will also be assessed at Week 4, Week 12, at every scheduled Follow-up Visit thereafter, and at the Week 108/Study Termination Visit. Clinical laboratory parameters to be assessed at the study visits are listed below:

Electrolyte Panel	Chemistry Panel	Hematology Panel
• Sodium	
 
Total bilirubin
 
	
 
Hemoglobin
 

 
Potassium
 
	
 
Alkaline phosphatase
 
	
 
Hematocrit
 

 
Bicarbonate
 
	
 
Alanine aminotransferase
 
	
 
Red blood cell count
 

 
Chloride
 
	
 
Aspartate aminotransferase
 
	
 
Red blood cell morphology
 

	
 
Urea nitrogen
 
	
 
White blood cell count
 

	
 
Creatinine
 
	
 
Platelet count
 

	• Calcium	
	
 
Albumin
 
	

Clinical laboratory results outside the normal reference range must be assessed for clinical significance by the Investigator. Clinically significant refers to a laboratory value that is unusual with respect to the subject's medical history or current health status. Clinically significant abnormal laboratory test values will be reported as AEs and treated and/or followed-up until the symptoms or values return to normal or acceptable levels, as judged by the Investigator. Where appropriate, medical tests and examinations will be performed to assess and document resolution.

A urine pregnancy test will be collected at every visit for females of childbearing potential. A positive pregnancy test will exclude the subject from further participation in the study. Pregnant subjects who are discontinued from the study will be transitioned to an alternate therapy at the discretion of the Investigator.

#### 3.3.2.4 Pulmonary Function Tests (PFTs)

Pulmonary Function Tests (PFTs) will be assessed at Baseline as part of the Study Termination (Week 16) assessments from protocol RIN-PH-201 and at Week 12, Week 48, and at Week 108/Study Termination. If the PFT is done both prior to and after a

bronchodilator, only the pre-bronchodilator values will be recorded. Pulmonary function tests should be conducted after recovery from the 6MWT.

The following parameters will be recorded (absolute values and % predicted): FEV1, FVC, TLC, and DLCO (uncorrected for hemoglobin and lung volume).

#### 3.3.2.5 Oxygenation

#### 3.3.2.5.1 Pulse Oximetry

Pulse oximetry will be assessed immediately prior to, throughout the conduct of, and immediately after each scheduled 6MWT assessment at Baseline (as part of the RIN-PH-201 Study Termination Visit), Week 4, Week 12, every 12 weeks thereafter, and at Study Termination. Pulse oximetry will include the collection of SpO2 and HR. The SpO2 and HR obtained immediately prior to and immediately following completion of the 6MWT will be recorded in the electronic case report form (eCRF). In addition, the lowest recorded SpO2 with the associated HR obtained during each 6MWT will be recorded in the eCRF.

When possible, pulse oximetry should be recorded using the provided pulse oximeter (Nonin 3150). In the event the provided pulse oximeter cannot be used (i.e., subject has known issues with obtaining accurate readings from a finger probe, etc.) an alternative device may be used with prior sponsor approval so long as the same device is used for all planned 6MWT.

#### 3.3.2.5.2 Supplemental Oxygen Requirement

The amount of supplemental oxygen (L/min) required at rest will be assessed at Baseline and at regularly scheduled visits. The amount of supplemental oxygen required at the 6MWT assessment will also be recorded for each 6MWT assessment.

#### 3.3.2.6 Adverse Events

Any AEs that are ongoing at the Study Termination Visit for the RIN-PH-201 study should be recorded as continuing AEs in this open-label study.

Adverse events will be recorded throughout the course of the study from the time that each subject signs the ICF until the subject is either discontinued from the study or all Study Termination assessments have been completed. Each subject will be questioned for AEs at

each scheduled study visit and during required telephone/email contacts. Subjects will also be instructed to spontaneously report all AEs throughout the study.

All AEs should be followed until either resolution (or return to normal or Baseline values), until they are judged by the Investigator to no longer be clinically significant, or for at least 30 days if the AE extends beyond the final study visit. All AEs meeting the criteria for serious (*i.e.*, serious adverse events [SAEs]) should be followed until resolution, death, or the subject is lost to follow-up even if they are ongoing more than 30 days after completion of the final study visit (Study Termination). All AEs/SAEs that occur while the subject is on study drug will be recorded as instructed in this protocol.

Sections 9 and 15.2 provide the guidelines and definitions for recording AEs.

#### 3.3.2.7 Concomitant Medications

All concomitant medications taken during the conduct of the study, including those taken for AEs or other medical events, should be recorded in the subject's source documents and captured in the eCRF as required. Concomitant medications that were ongoing at the end of the RIN-PH-201 study will be recorded in the eCRF for the open-label study.

#### 3.3.2.8 Hospitalization due to Cardiopulmonary Indications

Hospitalizations due to cardiopulmonary indications must be recorded in the eCRF from the time of informed consent until study termination. Adverse events resulting in hospitalizations, regardless of cause or duration should also be recorded as SAEs per Appendix 15.2. Please note that, when possible, study medication should be continued during hospitalizations.

#### 3.3.2.9 Exacerbations of Underlying Lung Disease

An exacerbation of underlying lung disease is defined as an acute, clinically significant, respiratory deterioration characterized by evidence of new widespread alveolar abnormality (Collard 2016).

As adapted from the publication by Collard and colleagues (Collard 2016), the following diagnostic criteria may be used to help support a diagnosis of acute exacerbation:

- 1. Previous or concurrent diagnosis of ILD including CPFE
- 2. Acute worsening or development of dyspnea typically of less than one month duration
- 3. CT with new bilateral ground-glass opacity and/or consolidation superimposed on a background pattern consistent with usual interstitial pneumonia pattern
- 4. Deterioration not fully explained by cardiac failure or fluid overload

For the purposes of this protocol, events that are clinically considered to meet the definition of acute exacerbation but fail to meet all four diagnostic criteria due to missing CT data should still be considered an exacerbation for reporting purposes.

Exacerbations of underlying lung disease should be recorded throughout the duration of the study from the time of informed consent until study termination. Exacerbations of underlying lung disease will also be reported as AEs or SAEs per Appendix 15.2.

#### 3.3.2.10 Telephone/Email Contact

Weekly telephone/email contact is required for the first 12 weeks of the study to instruct the subject to titrate their dose of study drug and to assess for AEs and concomitant medications. After the first 12 weeks, telephone/email contact must occur at least monthly.

Telephone/email contact may be replaced by a face-to-face interaction on the weeks where study visits occur and the information can be obtained during the visit. The subject may be contacted via email in lieu of a telephone call; however, email should not replace direct follow-up by telephone or in clinic for clinically significant AEs or other emergent issues. All telephone or email contacts (*i.e.*, any dosing instructions, AEs reported and/or medication changes) with the subject must be noted in the source documentation.

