#### 10.3 ANALYSIS PLAN

All safety and efficacy data will be summarized in tables and listings and analyzed for trends over time. No formal hypothesis testing is planned.

The safety population will be defined as all subjects in the study that received inhaled treprostinil at any time during the course of the study. Safety analyses will be performed on the safety population. All AEs as recorded by the Investigators will be assigned MedDRA preferred terms by the sponsor for reporting purposes.

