5 SEQUENCE OF PLANNED ANALYSES

Along with the safety information from the parent study, safety information from the RIN-PH-202 study will be provided to the Data Monitoring Committee (DMC) periodically for safety review.

After study completion and unblinding for the parent study, a data cut for the RIN-PH-202 study will be performed to facilitate the analyses for the RIN-PH-201 study. Analyses based on additional data cuts and the final analyses at the time of study closing will be performed separately.

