11 SAFETY ANALYSES

11.1 ADVERSE EVENTS

AEs are captured from the time the Informed Consent Form is signed. Any AEs that are ongoing at the Study Termination Visit from study RIN-PH-201 are recorded as continuing AEs in the RIN-PH-202 study. All AEs with an onset date on or after the first dose of inhaled treprostinil in the RIN-PH-202 study or AEs ongoing from the parent study will be included in data listings and summaries.

The AEs will be coded using the Medical Dictionary for Regulatory Activities (MedDRA), and all summaries will utilize the Preferred Term (PT) and/or System Organ Class (SOC) to categorize AEs. All AEs will be organized by treatment group in the parent study and listed by subject, including onset date (day), cessation date (day), verbatim term, corresponding

SOC and PT, seriousness, date AE became serious, severity, frequency, relationship to study drug, action taken with study drug, and outcome.

The overall summary of AEs includes the number of subjects with any AE, the number of subjects with any study drug-related AEs, the number of subjects with AEs leading to study drug withdrawal, the number of subjects with AEs leading to death, the number of subjects with any serious AEs, and the number of subjects with any study drug-related serious AEs.

The summaries of AEs by SOC and PT will be provided by parent study treatment group and overall. The summaries of AEs, serious AEs, non-serious AEs, AEs probably or possibly related to inhaled treprostinil, and AEs leading to permanent discontinuation of inhaled treprostinil will include the number of subjects (percent of subjects) and number of events for each reported PT.

The total number of AEs and the AE rates will be calculated and summarized for each display, as appropriate. The AE rate will be calculated as the total number of AEs divided by the total patient years of exposure to study drug per treatment group in the parent study.

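### The pooled AE rate mixes weekly and at-least-monthly AE contact, so it may fall with longer follow-up partly as an artefact

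*Protocol*

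**What the plan says.** Protocol 3.3.2.10 states: "Weekly telephone/email contact is required for the first 12 weeks of the study". One stated purpose of these contacts is "to assess for AEs and concomitant medications". For the rest of the study, "After the first 12 weeks, telephone/email contact must occur at least monthly". A visit may stand in for a contact in weeks when one falls.

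Protocol 3.3.2.6 has subjects asked about AEs at "each scheduled study visit and during required telephone/email contacts". The same section tells subjects to report AEs unprompted throughout. Protocol 9.2 has onset and cessation dates recorded. Appendix 15.2 prescribes an opening question about how the subject is doing or feeling, with no look-back period.

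On analysis, Protocol 10.3 says: "All safety and efficacy data will be summarized in tables and listings and analyzed for trends over time". It plans no formal testing. SAP 11.1 says: "The AE rate will be calculated as the total number of AEs divided by the total patient years of exposure to study drug", with one figure per parent-study group. It also puts AEs still ongoing from RIN-PH-201 into the summaries. The AE tables listed in SAP 12.1 include breakdowns by severity and by dose at onset, but none by time on drug. SAP 5 plans a cut after the parent study is unblinded and adds: "Analyses based on additional data cuts and the final analyses at the time of study closing will be performed separately".

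**The concern.** The minimum frequency of AE questioning drops about 4.3-fold at Week 12, and the analysis takes no account of it. The longer the follow-up, the larger the share of patient-time under the sparser schedule. If monthly questioning misses some short, mild events that weekly questioning would catch, the pooled rate drifts down as follow-up accrues, even when the true rate is constant.

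Long-term safety is a secondary objective, and the study's one stated hypothesis (Protocol 1.4) concerns it. A lower rate later on drug, or at a later cut, could be read as good long-term tolerability when part of it came from asking less often. If capture does fall, the error runs in the drug's favour. Serious AEs, hospitalizations and deaths should be little affected.

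**Working it through.** The plan gives no AE rate or expected count, so there is no figure to reproduce. The check asks how far a change in capture alone could move the pooled rate.

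**Inputs from the documents.** Weekly contact for 12 weeks, then at least monthly (Protocol 3.3.2.10). Maximum follow-up 108 weeks (Protocol 3.1). Rate = all AEs / all patient-years (SAP 11.1).

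**Assumptions not in the documents.** The true AE rate is constant. Contact occurs at the required minimum. An AE is recorded only if recalled at the next contact, with recall decaying exponentially at half-life h. Earlier cuts are represented by 24 or 48 weeks of follow-up per subject; the SAP gives no such durations, and real follow-up would be staggered.

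**Step 1: contact density.** With 52.18 weeks per year, a month is 52.18/12 = 4.35 weeks. Weeks 1-12 have 12 contacts (1.00 per week). The remaining 96 weeks have 96/4.35 = about 22 (0.23 per week), a 4.3-fold drop. The share of follow-up under weekly contact is 12/24 = 50% at Week 24, 12/48 = 25% at Week 48 and 12/108 = 11% at Week 108.

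**Step 2: captured fraction.** For contact interval L and k = ln 2/h, capture = (1 - exp(-kL))/(kL). For h = 4, k = 0.1733:
- L = 1 gives 0.918.
- L = 4.35 gives 0.702.
- Relative capture r = 0.702/0.918 = 0.765.

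**Step 3: pooled rate at follow-up T, relative to Week 12.** P(T) = (12 + (T - 12)r)/T. For h = 4, P(24) = 0.883, P(48) = 0.824 and P(108) = 0.791. So P(108)/P(24) = 0.896 and P(108)/P(48) = 0.960.

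| h (weeks) | r | P(24) | P(48) | P(108) | 108 vs 24 | 108 vs 48 |
|---|---|---|---|---|---|---|
| 2 | 0.611 | 0.806 | 0.708 | 0.654 | 0.81 | 0.92 |
| 4 | 0.765 | 0.883 | 0.824 | 0.791 | 0.90 | 0.96 |
| 8 | 0.870 | 0.935 | 0.902 | 0.884 | 0.95 | 0.98 |
| 16 | 0.931 | 0.966 | 0.949 | 0.939 | 0.97 | 0.99 |
| complete capture | 1 | 1 | 1 | 1 | 1.00 | 1.00 |

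**Step 4: allow for reporting that does not depend on contact.** If a share s of AEs is always recorded, capture becomes s + (1 - s)(1 - exp(-kL))/(kL). With s = 0.5 and h = 2, r rises from 0.611 to 0.822, and the 108-week rate is 0.842/0.911 = 0.92 of the 24-week rate. With s = 0.8 and h = 2, r = 0.932 and the ratio is 0.940/0.966 = 0.97.

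**Step 5: rival explanations with no loss of capture.**
- Suppose the true rate in Weeks 1-12 is twice the later rate. In units of the later rate, the pooled rate is (24 + T - 12)/T, which is 1.50, 1.25 and 1.11 at Weeks 24, 48 and 108. The ratios are 1.11/1.50 = 0.74 and 1.11/1.25 = 0.89.
- Suppose the numerator includes one carried-over AE per subject and the true rate is 4 per year. The rate is 4 + 52.18/T, which is 6.17, 5.09 and 4.48 per year. The ratios are 4.48/6.17 = 0.73 and 4.48/5.09 = 0.88.

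On these illustrative values, either rival produces a larger decline than the recall model does.

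**The case against.** The strongest reply is that a longer gap between contacts changes how often AEs are asked about, not the period they cover. Each contact can collect everything since the last one, onset dates are recorded, and subjects must report spontaneously. Monthly is a floor: Protocol 7.3.1 allows more contact as needed, and Protocol 6.1 ties contact to dose adjustments. A reader might infer that AE rates must fall with time on drug by construction. The documents do not support that, because with complete capture there is no fall. What remains is that nothing in the plan makes capture equal in the two periods. The prescribed question sets no look-back period, and the only diary described is optional and tracks dosing.

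A second reply is that no text plans to compare pooled rates between cuts. That is correct: SAP 5 says only that those analyses are done separately, and the SAP specifies no AE time trend. The comparison it does lay out, by parent-study group, has both groups on the same contact schedule. But Protocol 10.3 commits to looking at all safety data over time, and successive pooled rates invite the comparison.

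A third reply is that recall loss should not be applied to the whole rate. The rate also contains serious AEs, exacerbations and laboratory findings made at visits. This stands, and it is why the no-spontaneous-reporting figures should be read as the larger end of the range. Finally, onset days are already listed and exploratory analyses are allowed, so the split could be made at reporting. That shows the change is cheap, but not that the plan provides for it.

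**Conclusion.** The concern holds in a limited form. The pooled AE rate mixes two ascertainment intensities whose weights shift with follow-up, and neither document acknowledges this. The rate may therefore decline over time or across cuts partly as an artefact, chiefly for mild, transient, non-serious AEs.

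The size is unknown. The range of 0.81 to 0.97 (against 24 weeks) or 0.92 to 0.99 (against 48 weeks) rests on the assumed half-lives, minimum contact, no spontaneous reporting and a constant true rate. Spontaneous reporting moves it towards 1.00. A reader might go on to treat any observed decline as under-reporting. That is not supported either: the recommended escalation table in Protocol 6.1 reaches its last row at Day 31, so a true early excess is plausible, and carried-over AEs also raise short-follow-up rates. Type I error, power and sample size are not affected, since no formal test is planned. This is a worthwhile, inexpensive improvement to the SAP, not a fault that undermines the study.

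**What to change.** In SAP 11.1:

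1. Report rates of new-onset AEs separately for onset on Study Days 1-85 and after Day 85, each over its own patient-years.
2. Show AEs ongoing from RIN-PH-201 separately and keep them out of these rates.
3. Base any statement about AE trend, over time or between cuts, on intervals after Day 85, where the minimum contact schedule is constant. Alternatively, base it on serious AEs, AEs leading to permanent discontinuation, hospitalizations and deaths, which depend little on contact frequency.
4. Footnote the change of contact schedule on the AE rate tables, and state that the Day 85 split cannot separate lower capture from a true early excess.

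The cost is SAP wording and one further split of existing tables, using onset dates already collected. The downside is more columns and less precision in each period.

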#### 3.3.2.11 Continued Access Plan

Subjects who have completed the Week 108/Study Termination Visit will be given the option for continued access to inhaled treprostinil. During Week 108/Study Termination Visit, the Investigator should assess each subject's eligibility for the Continued Access Plan.

